##### b. For prospective studies:

i.) Total number of subjects planned to be enrolled in the study at AEHN site(s): 140 screened in single session, with target of 100 meeting inclusion criteria for the full treatment study

ii) For multi-site projects, please indicate total number of subjects planned to be enrolled in the study at all sites: Of the 100 participants that will meet inclusion criteria for the full treatment study, approximately 60 will be recruited to the brain imaging (including both MRI and CT) study conducted at U. Penn. The rest will have already received brain scans through their

Albert Einstein Healthcare Network Einstein	AEHN Protocol/Summary		
	NUMBER	DATE	PAGE
	HRP-204	11/1/2011	7 of 27

participation in MMRI sponsored studies included the Moss Research Registry and conducted via the "Cognition and Action" or "Language and Aphasia" laboratories.

iii) Describe access to a population that would allow recruitment of the targeted number of subjects (*i.e. how many potential subjects do you have access to? What percentage of those potential subjects do you need to recruit?*) : Patients and controls will be recruited from the Moss Research Registry; the requisite approval has been obtained from Registry Coordinator. The registry contains medical records of patients who have already agreed to participate in studies, allowing us to pre-select patients based on the likelihood of meeting inclusion criteria. Patients will also be recruited using a flyer distributed by therapists in the clinical programs at MossRehab and by the research staff to participants in stroke support groups in the Philadelphia metropolitan area.

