#### C.7. THERAPY REGIMEN

**a. Group assignment:** A research assistant (RA), who will not be involved in any assessments, will assign patients to the MT or placebo therapy (identical therapy with an opaque divider rather than a mirror) using stratified randomization based on the patient's Fugl-Meyer score. Before starting the trial an assignment order will be developed based on whether a patient's pre-treatment Fugl-Meyer score was low (between 10 and 30) or moderate (between 30 and 50). A previous MT RCT using a similarly chronic patient population and an identical placebo therapy showed little benefit of the placebo therapy. Thus, we must consider a balance between the scientific requirements of an appropriate control group and the ethical considerations of using patients' time to complete a therapy that is known to be ineffective. To balance these considerations, we will assign patients to the MT and placebo treatment groups in a 2:1 ratio, respectively. This inequality in sample size will only reduce statistical power by approximately 3% [81]. In addition, patients assigned to placebo treatment will be given the option of being crossed over to receive MT after the three month assessment. Patients will not be aware of which therapy is the placebo because both therapies will be described as studying the role of visual feedback rather than a test of "mirror therapy." Both treatments will include 2 daily 30 minute

Albert Einstein Healthcare Network <hr/> Einstein	AEHN Protocol/Summary		
	NUMBER	DATE	PAGE
	HRP-204	11/1/2011	12 of 27

therapy sessions, 5 days per week over a 4 week period.

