**C.13. Testing Specific Aim 3 (predicting individual differences in therapeutic benefit)**

All tests of Specific Aim 3 will focus on data from the MT group only.

a. Testing predicted relationships between processes underlying MT and MT benefit using lesion location: We will examine the relationship between the change in primary and secondary outcome measures and lesion location using whole-brain voxel-based lesion-symptom mapping (VLSM) analyses [83]. VLSM measures whether a behavioral score systematically differs between participants with and without damage to each voxel under investigation. Tests of this difference use a t-statistic to describe the difference in means between the damaged-group and non-damaged-group while taking into account the variances within each group. The t-statistic is thus used as a convenient measure of group differences, without the intention of comparing it to the parametric t distribution. Instead, statistical significance will be determined by non-parametric permutation tests [84], in which the distribution used for inferential statistic calculations are created by sampling from the observed data rather than assuming an a priori distribution. Thresholds for significance will be calculated from the 95th percentile of this distribution, to ensure a family-wise false positive rate of 0.05 [84]. The total number of comparisons will also be reduced by only performing analyses on those voxels that are damaged in at least 10% of participants (to avoid undue influence of a small number of participants).

As in the previous measures, we will use an ANCOVA-like procedure to determine whether post-treatment scores (the DV) are affected by damage status to each individual voxel under consideration (the IV) after controlling for pre-treatment score and total lesion volume (covariates). Separate VLSM analyses will be done for each primary and secondary outcome

Albert Einstein Healthcare Network Einstein	AEHN Protocol/Summary		
	NUMBER	DATE	PAGE
	HRP-204	11/1/2011	16 of 27

measure. The voxels identified as being predictive of MT benefit using the VLSM analysis should be consistent with the a priori ROI predictions (Table 1). VLSM will also allow us to test whether voxels outside of these ROIs predict MT benefit.

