- b. Testing predicted relationships between processes underlying MT and MT benefit using behavioral scores: In addition to using VLSM to test how the proposed neural substrates of the four sensorimotor processes are able to predict MT's benefit, we will also use the confirmatory behavioral measures (our proxy for the integrity of the processes) to predict MT's benefit. We will use linear stepwise regression to predict post-treatment scores (the DV) using each behavioral measure (the second level predictor/ IV) after controlling for pre-treatment score (the first level predictor/ IV). Note that this analysis is identical to the ANCOVAs used above except that a continuous IV is used, thus requiring regression rather than ANOVA. Analyses will be done separately for each of the four processes and each primary and secondary outcome measure. Testing our predictions about the processes will involve examining the sign and significance of second level predictor's regression weight. For example, if poor proprioception leads to reduced benefit of MT (see B.2), the regression weight for RASP (where high score corresponds to better proprioception) will be significantly positive. Alternatively, if poor proprioception lead to increased benefit of MT, the regression weight will be significantly negative. Finally, if proprioception does not affect MT benefit, the regression weight will not significantly differ from zero. Determining the influence of action observation, visual-proprioception integration, and motor imagery will use the same logic.
- c. Testing predicted relationships between lesion areas and confirmatory behavioral measures  
As summarized in Table 1, we predict that damage to particular ROIs will cause deficits in particular sensorimotor processes, which we will assess using the confirmatory behavioral tests. We will test these predictions in two ways. First, we will use t-tests to determine whether the pre-treatment confirmatory behavioral tests (the only time the tests are administered) will differ as a function of damage status to a particular ROI (using a 20% of volume criteria). Second, we will use linear stepwise regression to predict behavioral measure scores using percent damage to each predicted ROI after first controlling for total lesion volume. We have previously used both approaches successfully in a study of action observation [68].

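### The Table 1 regions have no region-level test against mirror-therapy benefit, and agreement with them has no criterion

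*Combined protocol and SAP*

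**What the plan says.** Aim 3 is restricted to one arm: "All tests of Specific Aim 3 will focus on data from the MT group only". C.13.a relates lesion location to change in each primary and secondary outcome by whole-brain voxel-based lesion-symptom mapping (VLSM). The model takes post-treatment score as the dependent variable, "controlling for pre-treatment score and total lesion volume (covariates". The search covers every sufficiently damaged voxel, by "only performing analyses on those voxels that are damaged in at least 10% of participants", and the permutation threshold is set "to ensure a family-wise false positive rate of 0.05". The only link to the predicted regions is the closing remark: "The voxels identified as being predictive of MT benefit using the VLSM analysis should be consistent with the a priori ROI predictions (Table 1".

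Table 1 names eight distinct regions for four processes: IFG, IPL, pMTG, SI, SII, BA5, BG and PM. IPL is listed for three of the four.

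Region-level measures do exist, in C.13.c. One is a t-test on damage status with a 20%-of-volume cut. The other is a regression to "predict behavioral measure scores using percent damage to each predicted ROI after first controlling for total lesion volume". In both, the dependent variable is a pre-treatment process test, not post-treatment outcome.

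**The concern.** B.1 and B.2 present the competing predictions about mechanism as the innovative part of the project, and the heading of C.13.a promises to test them with lesion data. The analysis under that heading asks a different question: does any voxel anywhere pass a whole-brain threshold?

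Two problems follow.

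- A true effect of a predicted region has to clear a threshold set by the whole search volume, although only eight regions were named in advance.
- The comparison with Table 1 has no decision rule. Significant voxels partly inside and partly outside the named regions could be called consistent or inconsistent, and no error rate attaches to that judgement.

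C.13.b tests process scores against benefit, and C.13.c tests regions against process scores. The direct link from region to benefit has no dedicated test. What is at stake is the interpretation of Aim 3. The Aim 1 treatment comparison is unaffected.

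**Working it through.** The documents state no effect size, power or effective number of tests for Aim 3, so there is no figure to reproduce. The calculation shows what the choice of threshold costs under stated assumptions.

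**Inputs from the documents**
- 100 treated patients (section 5.b: "Of the 100 participants that will meet inclusion criteria for the full treatment study") and 2:1 allocation (C.7.a: "we will assign patients to the MT and placebo treatment groups in a 2:1 ratio, respectively"), so 100 × 2/3 ≈ 67 MT patients.
- Two covariates plus one lesion term, so residual df = 67 − 1 − 2 − 1 = 63.
- Voxel filter: 10% of 67 ≈ 7 patients.
- Eight regions, counted from Table 1.

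**Assumptions**
- All 67 have usable lesion maps.
- Partial correlation r between lesion measure and outcome is 0.35 or 0.40, the same for a voxel as for its region.
- The whole-brain threshold is equivalent to m = 50 to 500 independent tests.
- Tests are two-sided; the plan does not state sidedness.

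**Formula.** Critical value: t at 0.05/m, two-sided, df 63. Effect: f = r/√(1 − r²), which is 0.374 at r = 0.35 and 0.436 at r = 0.40. Noncentrality: λ = f√63 (2.97 and 3.46) or f√67 (3.06 and 3.57), depending on convention. Power is the noncentral t tail beyond the critical value. Each range below spans the two conventions.

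| Test | Critical \|t\| | Power, r = 0.35 | Power, r = 0.40 |
|---|---|---|---|
| Eight regions, m = 8 | 2.83 | 56-59% | 74-77% |
| Whole brain, m = 50 | 3.45 | 33-36% | 51-55% |
| Whole brain, m = 500 | 4.15 | 14-16% | 26-30% |

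With λ = f√63, the relative loss at r = 0.40 and m = 50 is 1 − 0.510/0.735 = 31%. At r = 0.35 and m = 500 it is 1 − 0.136/0.557 = 76%.

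**On a standardized-difference scale.** Take a region damaged in 30% of patients (20 v 47), so λ = d√(20 × 47/67) = 3.75d. Then 80% power needs d = 0.98 with eight region tests, and d = 1.21 to 1.34 with 100 to 500 whole-brain tests.

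**Cross-check without assuming m.** Lesions were simulated on a 20 × 24 × 20 grid with 67 patients, the 10% filter, 300 permutations and no covariates. There were 150 runs per cell, so Monte Carlo error is up to about 8 points. The threshold averaged about 4.1, equivalent to roughly 420 to 440 tests. Detection inside the true region, whole-brain v region test:

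| d | Effect follows 20% region damage | Effect at one focal voxel |
|---|---|---|
| 0.5 | 6% v 17% | 6% v 5% |
| 0.8 | 20% v 41% | 23% v 23% |
| 1.0 | 40% v 63% | 34% v 43% |
| 1.2 | 65% v 89% | 41% v 48% |

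**Joint or separate regions.** Entering all eight regions together leaves df = 67 − 1 − 2 − 8 = 56. With λ = f√56 and alpha 0.05/8, power falls to about 49% (r = 0.35) and 66% (r = 0.40), before any loss from correlation between regions. The added test should therefore take one region at a time.

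**The case against.** The best defence is in B.3. It says that the evidence behind Table 1 is incomplete and often conflicting, and that whole-brain mapping was chosen so as not to lean on it. That is a sound reason to run VLSM and not to demote it. It is no reason to omit a region test alongside it.

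Three stronger readings are tempting, and the documents do not support them.

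- *A reader might infer that the Table 1 regions are never tested against benefit.* They are. Any of their voxels that pass the damage filter lie inside the search, and a surviving voxel is valid, if conservative, evidence. Only the overall judgement of agreement lacks an error rate.
- *A reader might infer that most of the power is wasted.* This is not shown. Effect size and effective number of tests are both assumed. Several scenarios lose less than half, and the difference is small when the critical site is focal, because averaging over a region dilutes the effect. The analytic comparison also counts a single voxel, whereas any surviving voxel in the region would count.
- *A reader might infer that a missed region would be taken as evidence against its mechanism.* C.13.a does not say so. The plan reads a null result that way only for the behavioral regressions in C.13.b.

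It also stands that this is a secondary, mechanistic aim, and that C.13.b already provides a process-specific test of benefit.

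**Conclusion.** The concern holds in a limited form. The eight predicted regions lack a dedicated test against post-treatment score, and the check against Table 1 has no criterion, although the measures needed are already derived.

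For an effect spread across a region, dedicated tests would raise power from about 14-36% to 56-59% at partial r 0.35, and from about 26-55% to 74-77% at 0.40. These figures rest on 67 MT patients with lesion maps and 50 to 500 effective whole-brain tests, and they show what is plausible rather than what to expect. They do not carry over to VRLAT, which is measured in right-hemisphere patients only and so has fewer patients. The change is a worthwhile, cheap improvement; the planned VLSM remains valid.

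**What to change.** Keep whole-brain VLSM at family-wise 0.05 as written, and add to C.13.a:

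1. For each outcome, regress post-treatment score on pre-treatment score, total lesion volume and percent damage to one Table 1 region at a time, in the MT group, with Holm correction over the eight regions.
2. Base the statement about agreement with Table 1 on these eight tests, in place of the informal check. Report VLSM findings inside and outside the regions alongside them.
3. State that an IPL result cannot separate the three processes that list it, and that the VRLAT models use right-hemisphere patients only.

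This needs no new data, since C.13.c already derives percent damage per region. The downside is one additional family of tests. Holm over eight controls error within an outcome, not across the four primary and four secondary outcomes, and the text should say so.

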### B. 4. Converging evidence between lesion location and other behavioral tests

In addition to making predictions about the integrity of the four processes that may underlie MT's benefit based on lesion location, we will measure performance on confirmatory behavioral tests to (1) provide further evidence about the neural substrates of these functions and (2) allow clinicians to have simple behavioral tests to predict individual differences in MT response without having to rely on lesion location information. All behavioral tests have been previously used in our labs. For action observation, we will use a test that involves viewing sequentially presented video pairs of actions, with the patient making same/different judgments about the actions [68]. For proprioceptive feedback, we will use the RASP [69], a standard clinical measure of proprioception that will also be a primary outcome measure. For visual-proprioceptive feedback, we will use a visual-analogue scale of initial mirror illusion sensation (rate how strongly it feels as if the arm you see in the mirror is actually the arm behind the mirror) and a simple judgment task (Parson's task [70]) that has been shown to require integration of visual and proprioceptive input. In this task, patients judge whether a visually presented hand is a left or right hand. These judgments are affected by the orientation of the participant's own hand, suggesting the decision is based on the seen and felt position of the body. We will have patients make verbal judgments while we systematically manipulate the orientation of the patients' hand. Finally, motor imagery will be assessed using consistency

Albert Einstein Healthcare Network Einstein	AEHN Protocol/Summary		
	NUMBER	DATE	PAGE
	HRP-204	11/1/2011	6 of 27

on a grasping imagery task [71] in which patients report how they imagine they would grasp a handle (overhand or underhand) and compare the imagined results to their actual grasping of an object. Table 1 summarizes the preceding three sections.

PROCESS	NEURAL SUBSTRATE	CONFIRMATORY BEHAVIORAL TEST
Action observation	IFG, IPL, pMTG	Spatial action recognition task
Proprioceptive feedback	SI, SII	RASP
Visual-proprioceptive integration	IPL, BA5	Parson's task, screening questionnaire
Motor imagery	IPL, BG, PM	Imagined grasping

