**d. Study Endpoints:**

Albert Einstein Healthcare Network <hr/> Einstein	AEHN Protocol/Summary		
	NUMBER	DATE	PAGE
	HRP-204	11/1/2011	10 of 27

- i. Describe the primary and secondary study endpoints (*i.e. the outcome(s) that the study is designed to evaluate*): Overall, the study will examine motor functioning of the impaired arm as well as sensation in the limb as well as hemispatial neglect (participants with right hemisphere lesions only). The primary outcome measures will be the (1) upper extremity portion of the Fugl-Meyer test, a standard clinical measure of arm motor impairment, (2), Action Research Arm Test (ARAT), a valid and reliable measure of arm function in simulated ADLs, (3) the Rivermead Assessment of Somatosensory Performance (RASP), which tests proprioception, two-point discrimination, surface pressure touch, surface localization, and tactile extinction [121], and (4) in right hemisphere patients only, a virtual-reality assessment of navigation (VRLAT) developed by [name] [77], which is more sensitive to mild forms of hemispatial neglect than paper-and-pencil tests. Secondary outcome measures will be (1) the Stroke Impact Scale, a self-report measure of use of limb in activities of daily living (2) timed finger tapping, (3) maximum grip and pinch force, as assessed using a dynamometer, and (4) the Wolf Motor Function Test [78] to assess function limitations and allow comparison with the results of CIMT (used as a secondary measure because patients with lower Fugl-Meyer score will not be able to complete many items on this test).
- ii. Describe any primary or secondary safety endpoints (*e.g. any disease or symptom that would result in the withdrawal of that subject from the study*): N/A

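### C.13.b names RASP, with no subscore, as both the proprioception predictor and an outcome: used as one score, its weight on the RASP outcome cannot be estimated, and on other outcomes it does not isolate proprioception

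*Combined protocol and SAP*

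**What the plan says.** B.4 assigns one behavioral test to the proprioceptive process: "For proprioceptive feedback, we will use the RASP [69], a standard clinical measure of proprioception that will also be a primary outcome measure". Table 1 repeats this and lists no other behavioral test for that process. Section 6.d.i makes RASP primary outcome 3 and describes it as a battery "which tests proprioception, two-point discrimination, surface pressure touch, surface localization, and tactile extinction". C.5 gives the same description.

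C.13.b predicts post-treatment scores "using each behavioral measure (the second level predictor/ IV) after controlling for pre-treatment score (the first level predictor/ IV"), in the MT group only. The scope has no exception: "Analyses will be done separately for each of the four processes and each primary and secondary outcome measure". The test is the sign and significance of the second-level weight. Under one hypothesis, "the regression weight for RASP (where high score corresponds to better proprioception) will be significantly positive"; under the opposite one it is significantly negative; and "if proprioception does not affect MT benefit, the regression weight will not significantly differ from zero".

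On timing, C.13.c refers to "the pre-treatment confirmatory behavioral tests (the only time the tests are administered"), and C.5 puts the Table 1 tests in the same pre-treatment assessment as the outcome measures. The summary of tests in 6.e.iii lists RASP once, among the assessment tests. Nothing describes a second pre-treatment RASP measurement kept for use as a predictor, and no section names a RASP proprioception subscore.

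**The concern.** B.2 sets out two opposite predictions: poor proprioception may weaken the response to MT, or it may strengthen it because there is less conflict with the mirror image. C.13.b is where the behavioral data are meant to decide between them, and B.4 wants the same tests to help clinicians predict response.

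There are two difficulties. For the RASP outcome, the adjustment covariate and the predictor under test appear to be the same number, which leaves nothing to test. For the other outcomes, the argument in B.2 is specific to proprioception as the only feedback about the hidden arm, but the score named covers touch and extinction as well. A weight on that score could be credited to the wrong process.

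**Working it through.** The documents give no sample size, power or alpha for C.13.b, so there is no figure of the plan's to reproduce. The first check below is algebra. The second is an illustration that rests on assumptions.

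**RASP as outcome.** Let P be pre-treatment RASP. The first-level predictor is P. The second-level predictor, RASP measured before treatment, is also P. The model is

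post-RASP = b0 + b1·P + b2·P + error = b0 + (b1 + b2)·P + error.

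Only the sum b1 + b2 is identified. A design matrix with columns (1, P, P), built for n = 67 (100 × 2/3, from the target of 100 and the 2:1 allocation), has rank 2 where 3 is needed. This holds at any n. The slope that remains cannot replace b2, because it mixes the stability of RASP over time with any effect of proprioception on benefit.

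Extent: 6.d.i lists 4 primary and 4 secondary outcomes, taking grip and pinch force as the single item listed. That is 1 of 8 outcomes for the proprioception process, and 1 of 4 × 8 = 32 process-by-outcome analyses.

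**Other outcomes.** Here the model has full rank, and the question is what the weight means. A simulation took the case in which proprioception has no effect at all. Its assumptions are not from the documents: five equally weighted standardized domains with common correlation r; an outcome baseline independent of RASP with weight 0.7; a standardized effect of 0.4 for the mean of the four other domains; residual SD 0.7; n = 67; two-sided 0.05; 3,000 runs per setting. The entries are the proportion of runs in which the predictor is significant.

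| r | RASP total | Proprioception subscore alone | Subscore, other domains as covariate |
|---|---|---|---|
| 0 | 0.97 | 0.06 | 0.05 |
| 0.3 | 0.99 | 0.42 | 0.05 |
| 0.5 | 0.99 | 0.74 | 0.04 |
| 0.7 | 0.99 | 0.90 | 0.06 |

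The total picks up the touch effect nearly always. The subscore alone avoids this only if the domains are uncorrelated. With the other domains in the model, the rate stays near 0.05.

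**Can a subscore model be estimated?** Under the same structure:

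- Subscore with baseline RASP total as covariate: squared correlation = (1 + 4r)/5, so the variance inflation factor (VIF) = 1.25/(1 − r). This gives 1.25, 1.79, 2.50 and 4.17 for r = 0, 0.3, 0.5 and 0.7. The model can be fitted, but the predictor is part of its own covariate.
- Subscore with the mean of the other four domains as covariate: squared correlation = 4r²/(1 + 3r), which is 0, 0.36/1.9 = 0.189, 1/2.5 = 0.400 and 1.96/3.1 = 0.632. The VIF is 1.00, 1.23, 1.67 and 2.72. At a given residual variance the standard error grows by the square root: 1.00, 1.11, 1.29 and 1.65.

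**The case against.** The strongest reply is that RASP in C.13.b may be shorthand for a proprioception score. B.4 calls it a measure of proprioception, and C.13.b says that a high score means better proprioception. With a subscore as predictor the RASP model can be estimated, as the VIFs show. This stands to the extent that non-estimability depends on one score filling both roles. But no section names a subscore, and the citations do not settle the scoring: reference 69 in the list is a memory test, and the reference 121 given for the battery lies beyond the end of the list. Even if a subscore was meant, it is not separated from correlated touch domains unless the analysis adjusts for them.

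The scope is also limited, and this stands in full. The problem lies in one process of Aim 3. The Aim 1 ANCOVA is untouched, the motor outcomes still allow a fitted model, and the lesion analyses approach the proprioceptive process by another route. C.13.b itself calls the behavioral tests proxies.

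A reader might infer three further things that the documents do not support:

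- That the failed model would be reported as no effect of proprioception. The plan's rule concerns an estimated weight that is not significant. A duplicated predictor gives no weight or p-value, so the gap would be visible.
- That B.2 attaches its strongest claim of novelty to this competing prediction. It attaches that claim to advancing a therapy for patients who respond poorly to others. Of the counter-intuitive prediction it says only that confirmation would be especially noteworthy.
- That touch deficits will be credited to proprioception at the simulated rates. The documents give neither inter-domain correlations nor domain effects, so the supportable word is could.

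**Conclusion.** The point holds, on two footings of different strength. If a single RASP score serves as both baseline and predictor, which is how the text reads with no subscore named, the second-level weight for the RASP outcome cannot be estimated. That is exact and needs no numerical assumption. It affects 1 of 8 outcomes for the proprioception process, which is also 1 of the 4 primary outcomes, in the MT group and in Aim 3 only.

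On the other seven outcomes, a significant weight on a multi-domain RASP score does not show that proprioception is responsible. That follows from the plan's own description of the battery. How often it would mislead is unknown, and the simulated 97% to 99% shows what is possible under a scenario in which only the other domains matter.

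The plan should be corrected before analysis, because choosing between a total and a subscore after seeing the data would be a free analytic choice. It does not threaten the trial's main comparison.

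**What to change.** In Table 1 and C.13.b, name the pre-treatment RASP proprioception subscore as the predictor for the proprioceptive process, and enter the remaining RASP domains as a covariate. Naming the subscore without the covariate is not enough once the domains are correlated. The alternative is to keep the full RASP score, describe the predictor as somatosensation, and draw no conclusion specific to proprioception.

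For the RASP outcome, either omit the proprioception test or define the outcome as the non-proprioception subtests at both pre- and post-treatment. In the second option the baseline covariate is already the score on the other domains, so it also serves as the adjustment. State that no conclusion about proprioception is drawn from a model of RASP on RASP.

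The plan already describes RASP as testing all five domains, so the change should need no new assessment, provided that the subtests are scored and recorded separately; the documents do not say whether they are. A single subscore may be less reliable and have a narrower range than the battery, and the covariate costs precision when domains are correlated (in the illustration above, a standard error 1.11 to 1.65 times as large for correlations of 0.3 to 0.7).

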Finally, a previous study of MT [18] hypothesized that removing visual feedback of the impaired arm causes the perceptual-motor system to try to fill in that information using motor imagery. Given that other forms of motor imagery can be therapeutically beneficial, the authors proposed that motor imagery was similarly beneficial in MT. Data from a later RCT of mirror therapy calls this claim into question [20]. When MT was compared to the same therapy with a covered mirror, the results clearly indicated that MT benefited patients while the covered mirror therapy did not. However, in both forms of therapy vision of the impaired limb was blocked, and thus motor imagery would be called upon in both. We will test whether MT's benefit is predicted by motor imagery ability (see C.13 for details).

In summary, we will test competing predictions about the mechanism of MT by utilizing individual differences in the integrity of four sensorimotor processes (action observation, proprioceptive feedback, visual/proprioceptive integration, and motor imagery) that may underlie MT's benefit.

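### C.13.b tests each process alone over 32–40 regressions with no lead outcome or error control, so it cannot support a claim about which process is the mechanism

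*Combined protocol and SAP*

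**What the plan says.** Section B.2 sets the purpose: "we will test competing predictions about the mechanism of MT by utilizing individual differences in the integrity of four sensorimotor processes". The processes are action observation, proprioceptive feedback, visual-proprioceptive integration and motor imagery. Table 1 (section B.4) gives one behavioral test for each, except that integration has two: "Parson's task, screening questionnaire".

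Section C.13.b predicts post-treatment scores "using each behavioral measure (the second level predictor/ IV) after controlling for pre-treatment score (the first level predictor/ IV"). On repetition it says: "Analyses will be done separately for each of the four processes and each primary and secondary outcome measure". The decision rule is: "Testing our predictions about the processes will involve examining the sign and significance of second level predictor's regression weight". The regressions are called stepwise, but the steps are the pre-treatment score and then one behavioral measure, so two processes never enter the same model.

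C.13.b gives no significance level, multiplicity adjustment, lead outcome or lead visit. Section 6.d lists four primary outcomes (Fugl-Meyer, ARAT, RASP, and VRLAT in right-hemisphere patients only) and four secondary outcomes. Section 6.c gives two post-treatment visits, 1 day and 3 months; C.13.b does not say which it uses. All of C.13 is limited to the mirror therapy group.

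**The concern.** There are two separate problems.

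First, a one-process model cannot tell a process that drives benefit from one that is merely correlated with it. The plan gives some reason to expect correlation: Table 1 lists the inferior parietal lobe as a substrate of three of the four processes. Total lesion volume, which is adjusted for in C.13.a and in the regressions of C.13.c, is not in the C.13.b model.

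Second, the rule is applied once per process (or score) per outcome, and nothing says how many significant weights, or on which outcome, would establish a process. One significant weight among dozens could be reported as support for a mechanism.

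At stake is the mechanistic conclusion of the third goal. The treatment comparison in C.11 is unaffected.

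**Working it through.** The plan states no error rate, test count or power for C.13.b, so there is no figure to reproduce.

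**Inputs from the document.** Four processes and five behavioral scores (Table 1); eight outcomes (section 6.d); two post-treatment visits (section 6.c); target of 100 patients (section 5.b) allocated 2:1 (C.7.a), so 100 × 2/3 ≈ 67 in the mirror therapy group.

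**Assumptions, not in the document.** Two-sided 0.05 per test; correlations among scores of 0.3–0.5 and among outcomes of 0.3–0.7; for one truly predictive process, a partial correlation with outcome (given the pre-treatment score) of 0.30–0.40.

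**1. Count.** 4 × 8 = 32; 5 × 8 = 40. Both visits: 64–80. Scoring grip and pinch separately gives nine outcomes: 36–45 at one visit.

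**2. Chance findings with no true effect.**
- Expected number: 0.05 × 32 = 1.6; 0.05 × 40 = 2.0. This does not depend on correlation.
- At least one, independent tests: 1 − 0.95^32 = 0.806; 1 − 0.95^40 = 0.871.
- At least one, correlated tests (simulation, n = 67, correlations as above): 0.51–0.73 for 32 tests and 0.58–0.81 for 40.

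**3. A process with no effect of its own.** If the true process has partial correlation r and another score correlates ρ with it, the second score's partial correlation in its own one-process model is ρ × r. The noncentrality is ρr/√(1 − (ρr)²) × √65, tested on 64 degrees of freedom:

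| ρ | r | ρ × r | Significant, separate model |
|---|---|---|---|
| 0.3 | 0.30 | 0.09 | 11% |
| 0.3 | 0.40 | 0.12 | 16% |
| 0.5 | 0.30 | 0.15 | 23% |
| 0.5 | 0.40 | 0.20 | 37% |

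Simulation agrees with these figures. With all four processes in one model, the rate is about 5% in every row.

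**4. Is the joint model enough alone?** No. With three null processes over eight outcomes, the simulated chance of at least one false finding in joint models is still about 55–58%. Multiplicity needs its own remedy.

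**5. Power cost.** For r = 0.3, a single uncorrected test has power of about 70%. In a joint model of four equally correlated scores the variance inflation is (1 + 2ρ)/[(1 − ρ)(1 + 3ρ)]: 1.6/(0.7 × 1.9) = 1.20 at ρ = 0.3, and 2.0/(0.5 × 2.5) = 1.60 at ρ = 0.5. The strictest Holm step is 0.05/4 = 0.0125. With 61 degrees of freedom and noncentrality 0.3145 × √(61/inflation), where 0.3145 = 0.3/√(1 − 0.09), power is about 38% at ρ = 0.3 and 27–28% at ρ = 0.5 (formula and simulation).

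**The case against.** Much of the case on the other side stands.

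- **Most predictions concern one process at a time.** In B.2, action observation contributes or does not, proprioception helps or hinders, and so on. B.4 also wants simple tests that let clinicians predict response. For prediction, the unadjusted association is the right quantity, and a correlated score is still a valid predictor. This limits the point to the mechanism wording of B.1 and B.2.
- **The correlations are not in the document.** B.3 itself describes the Table 1 regions as resting on incomplete and conflicting results. Proprioception is assigned SI and SII and shares no listed region with the other processes. At zero correlation the separate models give the nominal 5%. The size of the confounding is therefore conditional; the multiplicity is not.
- **There is converging evidence.** The lesion maps (C.13.a) and lesion-to-test checks (C.13.c) also inform interpretation. But agreement is not a decision rule, and shared parietal territory limits how well lesions can separate three of the processes.

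Two stronger readings should be resisted. A reader might infer that calling the behavioral tests confirmatory promises confirmatory inference. In B.1 and B.4 the word describes the instruments, as convergent checks on the lesion predictions. A reader might also infer that C.13.b falls short of a standard set by the lesion analysis, whose threshold is chosen "to ensure a family-wise false positive rate of 0.05". That threshold controls error across voxels within one map; the maps are also repeated for each outcome with no correction across outcomes.

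**Conclusion.** The point holds for C.13.b, and only for conclusions about mechanism. As written, the rule yields 1.6–2.0 expected chance findings at one visit if nothing predicts benefit, and it cannot separate a causal process from a correlated one. The chance of at least one false finding should be given as about 51–81% under the assumed correlations. The 81–87% figure requires independent tests, which is at odds with supposing correlated scores. The 11–16% and 23–37% rates for a process with no effect rest on assumed score correlations of 0.3 and 0.5, a true partial r of 0.30–0.40 and n of about 67; the VRLAT models would have fewer patients.

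That no correction is intended is read from the plan's silence. The document does not support saying that all of Aim 3 is uncorrected, or that the separate regressions are wrong for clinical prediction. This is an inexpensive improvement to a third-goal analysis.

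**What to change.** 1. Keep the separate regressions and label them as prediction and description.
2. For the mechanism claim, pre-specify one lead outcome that is not itself a process score, and one visit; Fugl-Meyer at 1 day is an example, being the first-listed primary outcome and the stratification variable. Fit one regression with the pre-treatment score and all four processes together. Choose in advance one score, or one combined score, for visual-proprioceptive integration, so that there are four tests.
3. Apply Holm over those four tests. Label all other outcomes and visits exploratory.
4. For the RASP outcome, do not enter the same RASP score as both baseline covariate and proprioception predictor. B.4 gives RASP both roles, and with one score in both the weight cannot be estimated.

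No new data are needed. The cost is wider intervals and lower power: for partial r = 0.3, about 38% (score correlation 0.3) or 28% (0.5) at the strictest Holm step, against about 70% for a single uncorrected test. The plan should state this, so that a non-significant weight is not read as showing that a process plays no part.
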